Frequency will be set to 100 Hz, which is known to generate comfortable sensations and reduce pain compared to lower frequencies (2-50 Hz). Stimulus amplitude and pulse duration will be increased until the subject reports that comfortable sensations cover the surgical site (region in which pain is anticipated following surgery). Stimulation parameters will be adjusted to improve stimulation coverage and comfort. Once optimum parameters have been determined, the needle will be withdrawn over the lead. The lead will be affixed to the skin with a sterile occlusive dressing (Figures 4 and 10). The stimulator will be set to deliver a range of currents. During their treatment, subjects can control these levels. Muscle strength will again be tested with the stimulator set for the optimal setting. The stimulator will be removed until after surgery.

Preoperatively, day of surgery. Subjects will continue to receive usual and customary local anesthetic-based analgesia. Because percutaneous PNS does not induce a sensory block and therefore does not provide anesthesia for the surgical procedure itself, we will continue to provide subjects with a preoperative single-injection local anesthetic-based peripheral nerve block (Table 1; 30 mL of ropivacaine 0.5% with epinephrine 1:400,000). In addition, surgeons will be permitted to infiltrate the surgical area with local anesthetic (bupivacaine HCl).

Figure 9. Ultrasound guided sciatic nerve lead insertion

Figure 10. Inserted electrical lead secured under gauze and dressing

Treatment group assignment (randomization). Subjects will be allocated to a treatment only after confirmation of successfully-inserted electrical leads and surgical procedure initiation; and will be randomized to one of two possible treatment groups (**Figure 11**):

- (1) **Current** delivered via the electrical lead(s) [Experimental group]
- (2) **No current** delivered via the electrical lead(s) [Control group]

Figure 11. Treatment groups.

Postoperative Day	0 [day of surgery]	1	2	3	4	5	6	7	8	9	10	11	12	13	14
Experimental	Electric current														
Control	No electric current														

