The 4-year UH3 Implementation Phase will include a multicenter, randomized, triple-masked, placebo-controlled, parallel-arm, human subjects pragmatic clinical trial. The primary Specific Aim of the trial is to determine the effect of percutaneous PNS on postoperative **opioid** requirements and **analgesia** following moderate-to-severely-painful ambulatory surgery (under the usual conditions in which PNS will be applied, making this a “pragmatic trial”). Secondary Specific Aims are to determine the effect of percutaneous PNS on physical and emotional **functioning, chronic pain, and quality of life** following moderate-to-severely-painful ambulatory surgery. The definitive UH3 pragmatic clinic trial will use the same protocol as the UG3 Planning Phase feasibility study described above, with the addition of any revisions determined necessary following that initial investigation. We will work closely with the NIH-DoD-VA Pain Management Collaboratory Coordinating Center at all phases of the definitive pragmatic clinical trial, from preparation through data analysis and manuscript preparation.

The primary end points will be cumulative opioid consumption and average surgical pain (measured with a Numeric Rating Scale) within the first 7 days following surgery. The primary analyses will compare the two treatment groups, one of which will receive active stimulation while the other will receive no stimulation.

Hypothesis 1 (UH3): Opioid consumption will be significantly decreased within the first 7 days following surgery with percutaneous PNS compared with usual and customary analgesia.

Opioid analgesic consumption [oxycodone 5 mg tablets] will be recorded at all time points (**Table 2**), ***with the primary end point being the cumulative opioid dose for postoperative days 0-7*** (see statistical section for further details).

Hypothesis 2 (UH3): Surgical pain will be decreased within the first 7 days following surgery with percutaneous PNS compared with usual and customary analgesia (measured with a Numeric Rating Scale).

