Current/present, worst, least, and average pain at the surgical site will be assessed using a Numeric Rating Scale (NRS) as part of the Brief Pain Inventory (short form). The Brief Pain Inventory is an approved NINDS common data elements Scale. The use of single items (e.g., average pain) in addition to the composite score is supported by the IMMPACT recommendations for assessing pain in clinical trials. The NRS will be recorded at all time points (**Table 2**), ***with the primary end point being the mean value of the “average” pain scores for postoperative days 0-7*** (see statistical section for further details). The NRS is a highly-sensitive measure of pain intensity with numbers

ranging from 0 to 10, zero equivalent to no pain and 10 equivalent to the worst imaginable pain. The NRS has been demonstrated to be a valid and reliable measure following analgesic interventions. In addition, NRS scores correlate well with other measures of pain intensity, and demonstrate high test-retest reliability. These NRS characteristics led to recent IMMPACT consensus recommendations for use of the 10-point NRS of pain intensity for pain trials.

An additional instrument, the Defense and Veterans Pain Rating Scale (DVPRS), will be utilized at various time points following surgery. The DVPRS was developed specifically for—and subsequently validated in—active duty military and Veteran patient populations. Unfortunately, this new instrument has not been validated for repeated measures, and therefore will not be used as a primary end point for the current investigation. However, future pain-related investigations involving military personnel and Veterans will undoubtedly use the DVPRS, and we want the results of the current study to be comparable. Therefore, we will use the DVPRS as a secondary end point at various time points (not all to lessen the questionnaire burden on subjects).

Primary end point: *In order to claim that percutaneous PNS is superior to usual and customary analgesia, at least one of Hypotheses 1 and 2 above must be superior while the other either superior or at least noninferior.*

Hypothesis 3 (UH3): Physical and emotional **functioning** will be significantly improved in the 12 months following ambulatory surgery with percutaneous PNS as compared with usual and customary analgesia (measured with the Brief Pain Inventory).

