We will first test for noninferiority of PNS to usual care on each of the two outcomes using 1-tailed noninferiority tests. The noninferiority deltas will be 1 point (worse) in pain score and 20% higher in opioid consumption. Noninferiority will be assessed at the overall 0.05 significance level with no adjustment to the significance criterion for testing two outcomes since noninferiority is required on both outcomes – i.e., an intersection union test. A noninferiority delta of 1 point in pain score is conservative since receiver operating characteristic curve analysis has demonstrated that changes from baseline of at least 1.7 along a 10-point NRS accurately identified patients who rated improvements as “much improved” or more, compared with those who perceived no change or worsening following analgesic interventions.^{153,156,177-179}

We will assess noninferiority on pain score using a one tailed t-test which incorporates the noninferiority delta of 1 point. The estimated treatment effect for pain score will be derived from a linear mixed effects model with the outcome of patient’s “average” pain score for each day, with fixed effects for intervention (PNS vs usual care) and time (days 1 through 7), and assuming an autoregressive correlation structure among and measurements on the same patient overtime. We will then test for noninferiority with a one tailed t-test in which the numerator is the estimated treatment effect from the model minus the noninferiority delta (1), and the denominator is the standard error of the estimated treatment effect. This method will yield results similar to comparing groups on the patient mean of these seven days, but is more flexible since it allows for missing data and also directly accounts for the correlation within patient. The model also allows assessing the treatment by time interaction, but this will most likely not be of interest.^{180,181}

Cumulative opioid consumption is not typically normally distributed, but usually approximates a log-normal distribution. We therefore plan to assess the treatment effect of PNS versus usual care on the log transformed cumulative consumption through POD 7 using a simple linear regression model (equivalent to a t-test). The estimated treatment effect (i.e., difference between groups) will then be used in a noninferiority test with null and alternative hypotheses as: $H_0: \mu_1 - \mu_2 \geq \log(1.2) =$

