Planning Phase sample size considerations. The sample size for the planning phase of 64 patients will be sufficient to estimate the treatment effects of interest with moderate precision, i.e., a confidence interval width of roughly 1.1 standard deviations for each outcome measure. Confidence interval width for a standard deviation estimate will be 0.70 standard deviations. The planning phase will be sufficient to use in estimating the expected treatment effect and standard deviation for each outcome for the larger trial.

UH3 Implementation Phase. Statistical methods for the UH3 Implementation Phase will follow very closely the methods described for the UG3 Planning Phase. The main difference is that UH3 Implementation Phase will have sufficient data to conduct the subgroup analyses and also considerably more power to assess the treatment effects of interest.

Another substantive difference from the planning phase is that in the full trial we will conduct interim analyses at each 25% of the planned enrollment using a group sequential method with gamma spending function and gamma parameter of -4 (quite conservative) for efficacy and 0 (moderately aggressive) for futility (**Figure 14**). The probability of crossing a boundary for either efficacy (mainly) or futility at the first through fourth looks would be 0.10, 0.42, 0.80 and 1.0, respectively, assuming the alternative hypotheses were true.

Figure 14. Stopping boundaries for 1-tailed tests for superiority for either pain score or opioid consumption. Blue region indicates superiority (reduced opioid consumption or pain score) and pink region indicates futility (lack of superiority). Z-statistic represents strength of evidence against the null hypothesis, either ratio of means or difference in means divided by standard error.

Missing outcomes data will be summarized along with the etiology of the absence. | While very little outcomes data is expected to be missing,

analyses will be intention to treat, and imputation of missing data using methods such as multiple imputation and last observation carried forward will therefore be utilized, based on the situation. In a conservative analysis imputation will involve the conservative approach of assigning the worst observed outcome to patients in intervention groups and best observed outcomes to those in control.

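### Last observation carried forward should not remain an option for the two primary endpoints: it can bias both, and the planned pain model does not need it

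*Combined protocol and SAP*

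**What the plan says.** All of the relevant text is in section 9.

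- **Missing outcomes (UH3 Implementation Phase).** The plan states that "imputation of missing data using methods such as multiple imputation and last observation carried forward will therefore be utilized, based on the situation". The rule covers outcomes data in general. The expectation is "While very little outcomes data is expected to be missing", with no percentage. A conservative analysis is added, "assigning the worst observed outcome to patients in intervention groups and best observed outcomes to those in control".
- **Pain analysis (Statistical Plan, UG3 part, carried over to UH3).** A linear mixed model with autoregressive correlation and "fixed effects for intervention (PNS vs usual care) and time (days 1 through 7"). It is preferred to comparing patient means partly because it "is more flexible since it allows for missing data".
- **Opioid analysis (same place).** Simple linear regression on log cumulative dose, described as equivalent to a t-test.
- **Endpoints (Hypotheses 1 and 2).** The "cumulative opioid dose for postoperative days 0-7", and the mean of the average "pain scores for postoperative days 0-7".
- **Assessments (Table 2).** Pain and previous-24-hour opioid use are recorded on days 0, 1, 2, 3, 4 and 7 within the primary window.
- **Nerve block (day-of-surgery paragraph).** For all subjects, "we will continue to provide subjects with a preoperative single-injection local anesthetic-based peripheral nerve block". Section 15 calls the local anesthetic long-acting. The first postoperative assessment is in the recovery room.

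**The concern.** Carrying a value forward assumes that a subject's pain or opioid use would have stayed where it was last seen. That is hard to defend in the first week after surgery. The recovery-room values follow a nerve block, the block wears off, and section 10 expects pain needing opioids to last about two weeks. A value from the block period would understate later days.

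Two consequences follow. If more subjects are lost early in one arm, that arm looks better than it is. If losses are equal but the arms differ less on the carried day than later, a real difference shrinks. Shrinkage also makes noninferiority easier to show if PNS is worse, and the joint claim requires noninferiority on both outcomes.

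The two parts of the plan also do not fit together. The pain model is chosen because it tolerates missing scores, and a later paragraph then calls for imputation. For cumulative dose there is no such model: a subject with one missing day has no total until something is filled in. The method of filling in therefore matters most there, and it is left open.

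**Working it through.** **1. The plan's own figure.** The documents give no number for missing data, so the only figure to reproduce is the sample size.

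- Inputs (UH3 sample size paragraph): 20% reduction, coefficient of variation 0.75, one-sided alpha 0.0125, power 90%.
- Log-scale SD = √ln(1 + 0.75²) = 0.668. Log-scale effect = ln 0.8 = −0.223.
- n per arm = 2 × (2.241 + 1.282)² × 0.668² / 0.223² ≈ 223, so 446 in total, against 448 stated.
- The step from 448 to 528 is attributed to the interim analyses alone. No allowance for dropout is stated in that calculation.

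**2. Bias in pain from unequal early loss, by formula.** Assume that subjects are lost right after day 1. Table 2 gives five scores in the model's window (days 1, 2, 3, 4, 7). The day-1 score is really observed, so only four of five values are imputed.

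- Shift in a lost subject's mean = 4/5 × gap between day 1 and the later mean.
- Bias in the arm difference = excess loss × 4/5 × gap.
- Low end: 0.02 × 0.8 × 2 = 0.03. High end: 0.06 × 0.8 × 3 = 0.14.

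The margin and the difference used for power are both 1 point, so this is 3% to 14% of either. Loss rates and gaps are assumptions.

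**3. Sensitivity to the block assumption.** Take assumed control means of 5, 5, 4.5 and 3.5 on days 2, 3, 4 and 7, and vary day 1.

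| Assumed day-1 mean | Five-visit mean | Shift per lost subject |
|---|---|---|
| 1 | 3.8 | −2.8 |
| 2 | 4.0 | −2.0 |
| 3 | 4.2 | −1.2 |
| 4 | 4.4 | −0.4 |

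If the block has little effect on day-1 scores, most of the problem disappears.

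**4. Simulation.** 264 per arm, day-1 mean 2, random loss after day 1, no true effect, one-sided nominal level 1.25%.

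| Loss, control vs PNS | Available-data mixed model: bias, rejection | Carried forward, mixed model | Carried forward, patient means |
|---|---|---|---|
| 5% vs 5% | 0.00, 1.2% | 0.00, 1.3% | no bias |
| 5% vs 10% | −0.01, 1.2% | −0.07, 3.0% | −0.08, 4.4% |
| 5% vs 15% | 0.00, 1.3% | −0.12, 7.5% | −0.17, 12% |

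The formula gives 0.05 × 2.0 = 0.10 for the 5-point imbalance. The simulated bias is somewhat smaller, because the mixed model weights visits unequally and because scores confined to 0–10 shift less.

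**5. Equal loss with a true effect.** Assume no difference on day 1 and −1.25 on later days. Patient-mean estimates move from −0.93 to −0.88 (5% lost), −0.92 to −0.83 (10%) and −0.92 to −0.74 (20%). The shrinkage roughly equals the fraction lost. Power stays at 98.9% or more.

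**6. Standard errors for pain.** With values carried forward, the mixed-model standard error against the empirical SD is 0.167 vs 0.168 at 5% loss and 0.169 vs 0.174 at 10%. With available data the model standard errors are 0.165 and 0.167, so carrying forward does not give smaller ones.

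**7. Opioids.** Assume 5 mg on day 1 and 72 mg over days 1–7. Carrying day 1 forward gives 7 × 5 = 35 mg, and ln(35/72) = −0.721. A 5-point excess loss in the PNS arm gives 0.05 × −0.721 = −0.036, a spurious geometric mean ratio of about 0.96. That is −0.036 / −0.223 = 16% of the planned effect on the log scale. Excess losses of 2 and 10 points give 0.99 and 0.93.

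**The case against.** The strongest reply is that little is at stake. The plan expects little missing data, excludes people who cannot be reached, contacts subjects daily or every other day while leads are in place, and masks subjects and assessors. The pain analysis is already a likelihood model, multiple imputation is listed, a worst/best-case analysis is planned, and nothing assigns carrying forward to the primary pain test. The UH3 statistical section is also due for revision after the pilot. All of this is correct, and it limits the size of the problem. It does not remove the option or supply a rule, and for cumulative dose there is no model to fall back on.

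It is also fair that the replacements are not a full cure. The mixed model and multiple imputation both assume missing at random. If subjects leave because of pain that was never recorded, both are biased too. They still need a weaker assumption than a flat course, and the worst/best-case analysis covers the remainder.

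Four stronger readings should be resisted:

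- **Standard errors too small.** Treating imputed values as observed can understate uncertainty in principle, but the simulation did not show it for pain. The case rests on bias.
- **Day-1 scores known to be suppressed by the block.** Block duration is not stated. Only the recovery-room value is clearly affected, and the pain model starts at day 1.
- **Unequal dropout to be expected.** Section 14 lists discomfort on insertion and/or during stimulation at 10%, and only one arm receives current, so it is possible. The documents do not predict it. The 7.5% and 12% rejection rates need a 10-point imbalance.
- **Days 5 and 6.** Table 2 does not assess them for anyone. That is a gap in the schedule for both arms, separate from dropout.

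**Conclusion.** The concern holds in a limited form. The plan permits last observation carried forward for both primary endpoints with no rule for its use. Over a changing postoperative week that can bias the comparison when early loss is unequal, and dilute a late-emerging difference when it is equal. For pain the method is also unnecessary, because the chosen model uses incomplete records. Log cumulative opioid dose is the more exposed endpoint.

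The likely size is modest: about 0.03 to 0.14 NRS points for a 2 to 6 point imbalance and, on one assumed dosing course, a geometric mean ratio of about 0.96 for a 5-point imbalance. These figures assume loss immediately after day 1, day-1 values well below later ones, and more loss under PNS. With little missing data, or a day-1 level close to later days, the effect is close to nil. The change is worth making because it costs almost nothing and removes an unsuitable option from the primary analyses.

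**What to change.** In the missing-data paragraph:

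- Delete last observation carried forward for the two primary endpoints, together with the choice by situation.
- State that pain is analysed with the planned mixed model on all available scores, without imputation.
- For opioids, multiply impute missing daily doses with arm, day, lead location and baseline in the model. Sum to the cumulative dose within each imputed data set, take logs, and combine the regression results.
- Imputation can draw only on days that someone observes. State separately one rule for days 5 and 6, the same in both arms.
- Keep the worst/best-case imputation as the sensitivity bound, and say that it is there because both main methods assume missing at random.

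The cost is SAP wording and a little more programming. Multiple imputation is already listed, and N stays at 528. The planned revision of the UH3 statistical section is a natural place for the change.

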In concert with the NIH-DoD-VA Pain Management Collaboratory Coordinating Center, the statistical section for the subsequent UH3 pragmatic clinical trial will be revised to reflect the **estimated treatment effect** and treatment group means. For the initial submission, we have estimated the probable maximum sample size for budgeting and planning purposes; but, the results of the initial feasibility study will most-likely decrease the definitive UH3 pragmatic trial required sample size. The statistical section and budget will be revised to reflect any changes. Any revisions to the protocol or informed consent forms will be submitted to the DSMB, individual center IRBs and funding center's oversight body. A manuscript with the results of the pilot study will be prepared and submitted with the results concurrently uploaded to ClinicalTrials.gov. Lastly, a final UG3 period report will be prepared for the funding and oversight agencies.

UG3 Planning Phase Specific Aims. The investigation described above will accomplish the two Specific Aims of the UG3 Planning Phase:

Specific Aim 1 (UG3): To determine the **feasibility** and **optimize** the protocol of the Implementation Phase (UH3) multicenter clinical trial that will compare percutaneous PNS with usual and customary opioid-based analgesia following moderate-to-severely painful ambulatory surgery.

Specific Aim 2 (UG3): To **estimate** the **treatment effect** of percutaneous PNS on pain and opioid consumption following moderate-to-severely painful ambulatory surgery compared with usual and customary opioid-based analgesia. This will allow determination of the required **sample size** of the definitive multicenter clinical trial of the Implementation Phase (UH3).

UH3 Implementation Phase

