Throughout, the significance level will be 0.05 for each hypothesis. SAS statistical software (Cary, NC) will be used for all analyses, and East 6.0 (Cytel, Inc. Cambridge, MA) for interim monitoring and sample size calculations.

UH3 Implementation Phase sample size considerations. Sample size parameters for the implementation phase will be derived from estimates in the planning phase. The sample size calculations below are conservative in that we observed a coefficient of variation for opioid consumption observed in our preliminary data of 0.48, substantially better than the assumed 0.65. It is thus quite possible that the actual sample size for the implementation phase will be smaller.

Sample size for the full trial will be chosen to allow an overall 90% power at the 0.025 significance level (since 1-tailed tests) to claim the intervention more effective than the control on postoperative opioid requirements and pain as measured by NRS pain score. In our joint hypothesis testing on these two outcomes, we power the study to have overall 90% power to detect superiority on either

outcome and at least noninferiority on both. We assume a coefficient of variation of 1.0 for opioid consumption and a standard deviation of 2 for pain score.

Power for the joint hypothesis testing will be driven by superiority tests since superiority is needed for at least 1 of the 2 outcomes. For cumulative opioid consumption through POD 3 our previous data had a coefficient of variation (CV) of 46% (mean (SD) of 28 (13) mg). Conservatively assuming a coefficient of variation of 75% through 7 days,¹⁸³ with a total N=528 we would have 90% power to detect a relative reduction of 20% in mean opioid consumption at the overall 0.025 significance level (0.0125 for each of the two 1-tailed tests for superiority), adjusting for interim analyses (N=448 before adjustment for interim analyses).

This sample size will yield high power (>0.95%) to detect superiority based on the intervention group having 1 point or more better than the control group on NRS pain score within the first 7 days, assuming a standard deviation of 2 points for mean of the “average” pain score for each patient.

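### The plan gives two different significance levels for the two primary superiority tests: 0.05 for each hypothesis, and one-sided 0.0125 each

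*Combined protocol and SAP*

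**What the plan says.** All of this is in section 9 of the combined protocol and SAP.

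- **General rule.** After the missing-data text of the UH3 Implementation Phase: "Throughout, the significance level will be 0.05 for each hypothesis". Sidedness is not given.
- **Sample-size text.** Directly afterwards, the trial is sized for 90% power at an overall one-sided 0.025, with "0.0125 for each of the two 1-tailed tests for superiority". N is 448 before and 528 after adjustment for interim analyses.
- **Numbered hypotheses.** Each primary outcome has its own number, for example "Hypothesis 1 (UH3): Opioid consumption will be significantly decreased within the first 7 days". Pain is Hypothesis 2.
- **Success rule.** "at least one of Hypotheses 1 and 2 above must be superior while the other either superior or at least noninferior".
- **Noninferiority.** "Noninferiority will be assessed at the overall 0.05 significance level with no adjustment to the significance criterion for testing two outcomes". These tests are one-tailed.
- **Interim monitoring.** Looks at each 25% of enrollment, gamma spending with parameter -4 for efficacy and 0 for futility. Figure 14 is captioned "Stopping boundaries for 1-tailed tests for superiority for either pain score or opioid consumption". The figure itself was not legible in the copy reviewed.
- **Coefficient of variation (CV) for opioid consumption.** The sample-size text describes three values as assumed: 0.65, 1.0 and 75%.

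**The concern.** Read as written, the general rule covers Hypotheses 1 and 2, and 0.05 for each is not 0.0125 for each. If 0.05 is meant as two-sided, it is 0.025 in the favourable direction, which is still twice 0.0125.

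The split is needed. Superiority on either outcome, with noninferiority on the other, supports the claim, so there are two routes to success. The argument for not adjusting the noninferiority tests is that both must succeed. It does not carry over to superiority, where one success is enough.

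The 0.0125 figure stands only in the sample-size text. The legible analysis text gives a level for noninferiority and none for superiority. An analyst who applies the only general testing rule would use 0.05, and for a band of results would reach the opposite primary conclusion. The same ambiguity affects the efficacy boundaries at every interim look.

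The three CVs are a lesser matter. They affect the stated power only if 1.0 is the intended value.

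**Working it through.** **Inputs from section 9.** 1:1 allocation; 90% power; 20% relative reduction, so effect ln(0.8) = -0.2231; CV 0.75; pain SD 2; four equally spaced looks; gamma -4 (efficacy) and 0 (futility).

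**Step 1: reproduce the stated N.** Log-scale variance = ln(1 + CV²) = ln(1.5625) = 0.4463 (SD 0.668). In the normal approximation,

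total N = 4 × 0.4463 × (z₀.₉₈₇₅ + z₀.₉₀)² / 0.2231² = 4 × 0.4463 × (2.241 + 1.282)² / 0.0498 ≈ 445,

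or 446 in equal groups. The t-test version gives 448, as stated. Numerical integration over four looks with non-binding futility gives an inflation factor of 1.177, and 448 × 1.177 = 527, against 528 stated. The cumulative stopping probabilities come out at 0.10, 0.43, 0.81 and 1.0, against 0.10, 0.42, 0.80 and 1.0 stated. Binding futility would give N of only 501-503.

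**Step 2: try every stated CV with every candidate level.** Fixed N / N after four looks:

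| CV | one-sided 0.0125 | one-sided 0.025 | one-sided 0.05 |
|---|---|---|---|
| 0.65 | 354 / 417 | 300 / 357 | 244 / 294 |
| 0.75 | **448 / 527** | 380 / 452 | 310 / 374 |
| 1.0 | 694 / 817 | 588 / 699 | 480 / 579 |

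Only CV 0.75 with one-sided 0.0125 gives the plan's figures.

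**Step 3: efficacy boundaries (gamma -4, four looks, non-binding futility).**

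| Level per test | Look 1 | Look 2 | Look 3 | Final |
|---|---|---|---|---|
| one-sided 0.0125 | 3.352 | 3.038 | 2.687 | 2.299 |
| 0.05 two-sided (0.025 one-sided) | 3.155 | 2.818 | 2.439 | 2.014 |
| one-sided 0.05 | 2.947 | 2.582 | 2.168 | 1.693 |

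**Step 4: results on which the rules disagree at the final look.** With N = 528, the standard error is 0.668 × √(4/528) = 0.0581 for log opioid consumption and 2 × √(4/528) = 0.174 for pain. The smallest significant opioid reduction is 1 - exp(-Z × 0.0581), and the smallest significant pain difference is Z × 0.174:

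| Final Z | Opioid reduction | Pain difference |
|---|---|---|
| 2.299 | 12.5% | 0.40 |
| 2.014 | 11.0% | 0.35 |
| 1.693 | 9.4% | 0.29 |

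Observed results between the first row and a lower row change verdict with the rule.

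**Step 5: false-claim rate with no true effect on either outcome.** For independent outcomes, ignoring the noninferiority requirement:

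- 0.0125 each: 1 - 0.9875² = 2.48%
- 0.025 each: 1 - 0.975² = 4.94%
- 0.05 each: 1 - 0.95² = 9.75%

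The documents give no correlation between the outcomes, so the full rule was simulated over a range (4,000,000 trials per correlation). It required superiority on one outcome and one-sided 0.05 noninferiority on the other at the same look, with margins ln(1.2) and 1 point, and futility was not enforced:

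| Correlation | 0.0125 | 0.05 two-sided | 0.05 one-sided |
|---|---|---|---|
| 0 | 2.4% | 4.7% | 9.3% |
| 0.5 | 2.3% | 4.5% | 8.8% |
| 0.7 | 2.1% | 4.2% | 8.1% |
| 0.9 | 1.8% | 3.5% | 6.8% |

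Both 0.05 readings exceed 2.5% at every correlation simulated, from -0.9 (2.6% and 5.9%) to 0.99 (2.8% and 5.6%). Using the plan's printed opioid margin of 0.263 gives 4.9% and 9.7% at correlation 0. Enforcing futility stops per outcome lowers the rates to 2.6-3.9% (two-sided) and 4.1-7.8% (one-sided) for correlations 0 to 0.9.

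**Step 6: the CV.** Power of the opioid superiority test for a 20% reduction at N = 528, with futility stops, is 90% at CV 0.75 and 73% at CV 1.0. At CV 1.0 the joint claim stays above 99% if both the 1-point pain benefit and the 20% opioid reduction are real.

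**The case against.** The strongest reply is that specific text governs general text. The sample-size paragraph names the two tests, their sidedness and the split, while the 0.05 sentence stands beside the software statement and may be meant for everything else. A related reading treats Hypotheses 1 and 2 as one joint claim at two-sided 0.05, hence 0.025 one-tailed overall and 0.0125 each. Both readings are plausible and agree with the sample size. Neither is written down. The sentence says each hypothesis, the two outcomes are numbered separately, and the text that would have to prevail describes how N was calculated.

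Figure 14 may plot boundaries at 0.0125. The stated first-look stopping probability of 0.10 leans that way (0.100 computed at 0.0125, 0.108 at 0.025, 0.115 at 0.05), though weakly. Even so, the 0.05 sentence would then contradict the figure.

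Some of the objection stands. One-sided 0.05 is the less likely reading, since the plan ties one-tailed superiority testing to 0.025; the realistic comparison is 2.01 against 2.30. The disputed bands lie well below the design effects of 20% and 1 point. Nothing is miscalculated in the plan's N. The section is also open to change: "the statistical section for the subsequent UH3 pragmatic clinical trial will be revised" after the feasibility study. That revision is described as covering the treatment effect and group means, not the significance level, but it is a convenient place for the correction.

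**Conclusion.** The contradiction is real, and the plan is wrong as written. The sample size shows that one-sided 0.0125 per superiority test is the design level; the general sentence permits a final critical Z of 2.01 or 1.69 instead of 2.30. Either 0.05 reading breaks the overall one-sided 2.5% on which the trial is sized.

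The critical values rest on four equal looks, gamma -4 and non-binding futility, which N = 528 supports. Binding futility would give 2.20, 1.91 and 1.58, in the same order. The false-claim rates also depend on the unknown correlation and on how the noninferiority and futility rules are applied, so they should be read as ranges. Figure 14 could not be checked.

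The CV inconsistency is secondary. The sentence giving N = 528 states its own 75%, so 0.65 and 1.0 look like leftovers unless 1.0 is intended.

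**What to change.** Before the first UH3 interim analysis:

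1. State in the analysis text that superiority under Hypotheses 1 and 2 is each tested at one-sided 0.0125 (overall one-sided 0.025), spent by the gamma -4 function over the four looks, and confirm that Figure 14 shows those boundaries.
2. Limit the 0.05 sentence to the remaining tests, giving sidedness, with noninferiority at one-sided 0.05 as already described.
3. Give 0.75 as the single planning CV pending the feasibility estimate, and delete 0.65 and 1.0. If 1.0 is intended, restate opioid-superiority power at N = 528 as about 72-73% (72% in the fixed design at 448).

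The cost is wording only, with no extra patients, and a stricter stated level for the two superiority tests. N would rise, to about 817, only if CV 1.0 is intended and 90% power for opioid superiority is to be kept.
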